4.5. TIMING OF ANALYSES

There will be no interim analyses in Phase 1b other than those associated with decisions pertaining to dose escalation and final determination of the MTD/RP2D.

The final analysis will occur at the End of Study as defined in section 4.4.4, where the clinical database has been cleaned, quality checked, and the database has been locked.

5. ANALYSIS POPULATIONS

The following analysis populations will be defined for this study: DLT Evaluable, Safety, Pharmacokinetic, Pharmacodynamic, and Efficacy Evaluable.

5.1. DLT EVALUABLE POPULATION

Patients will be evaluable for DLT in Part 1 if they meet the following criteria:

- They experience a DLT (as defined in Appendix 1 of the study protocol) after receiving ≥ 1 dose of LANRA during the DLT assessment period (Cycle 1, Day 1 until Cycle 2, Day 1).
- They receive at least 80% of the intended cumulative doses of LANRA and gilteritinib during the DLT assessment period without the occurrence of a DLT.

The DLT Evaluable Population will be used for all DLT data summaries.

5.2. SAFETY POPULATION

The Safety Population consists of all patients who receive ≥ 1 dose of either study drug and have at least 1 on-treatment safety-related observation, where a safety-related observation is defined as a reported AE or post-baseline assessment of vital signs, ECGs or safety laboratory assessments.

Patients will be analyzed according to their assigned dose level. The safety population will be used for all summaries of Safety data.

5.3. PHARMACOKINETIC POPULATION

The PK population consists of all patients with at least 1 post-dose LANRA plasma concentration.

Patients will be analyzed according to the dose level received at time of assessment. The PK population will be used for all summaries of PK data.

5.4. PHARMACODYNAMIC POPULATION

The PD population consists of all patients with baseline, and at least 1 post-dose pharmacodynamic assessment.

Patients will be analyzed according to the dose level received at the time of assessment. The PD population will be used for all summaries of PD data.

5.5. EFFICACY EVALUABLE POPULATION

The Efficacy Evaluable (EE) population will include all patients who receive ≥ 1 dose of either study drug and complete the first protocol-specified response assessment or have discontinued study treatment for toxicity or die prior to the first response assessment.

Patients in the EE population will be analyzed according to their assigned dose level. The EE population will be used for all summaries of efficacy data unless otherwise stated.

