## 12.0 Efficacy Assessments

Assessments that define the quality of response to study treatment will include physical examination, peripheral blood counts, and bone marrow examination. All assessments of response will be made by the investigator in accordance with ELN 2017 criteria ([Döhner 2017](#)). See [Appendix 2](#) for criteria that define each response category.

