### 12.1 Bone Marrow Examination

Perform bone marrow aspiration at Screening for morphology, karyotyping/fluorescence in situ hybridization (FISH) and biomarker assessments. A trephine bone marrow biopsy is required for patients in whom a satisfactory aspirate cannot be obtained (eg, due to dry tap, hypocellular or hemodiluted sample). Perform bone marrow aspirate (or biopsy) for response assessments and biomarker assessments ([Section 11.6](#)) on Day 1 of Cycle 2 and Cycle 3 and every 3 cycles thereafter (Cycle 6, Cycle 9, etc.) until CR/CRh is documented on 2 consecutive bone marrow examinations. At other times, perform bone marrow examination for confirmation of suspected progression/relapse.

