### 13.0 Criteria for Study Treatment Discontinuation

Study treatment will be discontinued for the following reasons:

- Unequivocal leukemic progression or recurrence of leukemia after a response
- Failure to achieve at least a PR after completion of 6 cycles of study treatment
- Pregnancy
- Death
- Withdrawal of consent
- A TEAE that:
  - is  $\geq$ Grade 3 and unresponsive to treatment modification guidelines outlined in [Table 2](#) and [Table 4](#) (for gilteritinib and LANRA non-hematologic toxicities, respectively) and [Table 5](#) (for hematologic toxicities associated with either or both drugs) OR,
  - chronic, Grade 1 or 2 toxicities that may not be tolerable when experienced for long periods of time either with or without treatment modification, thereby prompting the decision by the investigator, patient, or both to discontinue study treatment
- Need for, or use of a prohibited concomitant medication
- Hematopoietic stem cell transplantation
- Non-compliance with the study regimen
- Trial is discontinued by the study sponsor

Patients who discontinue study treatment must complete the End-of-Study Visit  $30 \pm 7$  days after the last dose of either gilteritinib or LANRA (whichever is later) or prior to initiation of new anticancer therapy.

During Part 1 (dose escalation), any dosing interruption resulting in administration of  $<80\%$  of the cumulative, Cycle 1 dose for either LANRA or gilteritinib in the absence of DLT will require the patient to be replaced.

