**Progressive Disease (PD):**

Evidence for an increase in bone marrow blast percentage and/or circulating blast counts as defined by at least one of the following:

- >50% increase in bone marrow blasts over baseline (a minimal absolute 15% increase is required in cases with <30% blasts at baseline) *or*
- Persistent bone marrow blast percentage >70% over  $\geq 3$  months without at least a 100% improvement in absolute neutrophil counts (ANC) to an absolute level  $>0.5 \times 10^9/L$  (500/ $\mu$ L) and/or platelet count to  $>50 \times 10^9/L$  (50,000/ $\mu$ L) without transfusion *or*
- >50% increase in circulating blasts to  $>25 \times 10^9/L$  (>25,000/ $\mu$ L) in the absence of Differentiation Syndrome\*\*\* *or*
- New extramedullary disease

\*\*\* Certain targeted therapies, for example, those inhibiting mutant IDH proteins, other kinase or targets may cause a Differentiation Syndrome, ie, a transient increase in the percentage of bone marrow blasts accompanied by an increase in circulating blasts. In the setting of therapy with such compounds, an increase in blasts may not necessarily indicate progressive disease. Such instances should be discussed with the study medical monitor on a case-by-case basis.

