6.5. EFFICACY ANALYSIS

Best response (CR, CRh, CRi, PR, MFLS, stable disease [SD], and progressive disease [PD]) will be summarized for the efficacy-evaluable population by frequency distributions and percentages in accordance with ELN 2017 criteria. Patients with no post-baseline response assessments will be considered non-responders. The 95% confidence interval (CI) for estimates of the proportion of patients with CR/CRh will be constructed with exact methods for the binomial distribution (eg Clopper-Pearson intervals). Additionally, 95% CIs for the estimates of the proportion of patients with any CR (CR, CRh or CRi) will be constructed in a similar manner.

Overall survival will be estimated using K-M methodology, including 95% CIs for quartiles. Minimal and maximal survival times will be computed by dose level. Patients alive at last follow-up will be censored at the date of last contact.

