10. PROPOSED TABLES, LISTINGS, AND FIGURES

Tables	
14.1.1	Subject Disposition and Discontinuation Summary, All Patients Enrolled: Phase 1b
14.1.2.1	Demographics, Safety Population : Phase 1b
14.1.2.2	Baseline Disease Characteristics, Safety Population : Phase 1b
14.1.4.1	Summary of Exposure, Safety Population: Phase 1b
14.1.4.2	Summary of Prior Antileukemic Regimens, Safety Population: Phase 1b
14.2.1	Summary of Best Response by ELN 2017 response criteria, Efficacy Evaluable Population: Phase 1b
14.2.2	Overall Survival, Safety Population: Phase 1b
14.3.1.1	Overview of Treatment Emergent Adverse Events, Safety Population: Phase 1b
14.3.1.2	Treatment-Emergent Adverse Events by System Organ Class, Preferred Term (All Cycles), Safety Population: Phase 1b
14.3.1.3	Treatment-Emergent Non-Serious Adverse Events by System Organ Class, Preferred Term (All Cycles), Safety Population: Phase 1b
14.3.1.4	Grade 3 or 4 Treatment-Emergent Adverse Events by System Organ Class, Preferred Term and Greatest Severity (All Cycles), Safety Population: Phase 1b
14.3.1.5	Treatment-Emergent Serious Adverse Events by System Organ Class, Preferred Term (All Cycles), Safety Population: Phase 1b
14.3.1.6	Treatment Related Adverse Events by System Organ Class, Preferred Term (All Cycles), Safety Population: Phase 1b

14.3.1.7	Treatment Emergent Adverse Events Leading to Dose Reduction by System Organ Class, Preferred Term (All Cycles), Safety Population: Phase 1b
14.3.1.8	Treatment Emergent Adverse Events Leading to Treatment Discontinuation by System Organ Class, Preferred Term (All Cycles), Safety Population: Phase 1b
14.3.1.9	Treatment Emergent Adverse Events Leading to Death by System Organ Class, Preferred Term (All Cycles), Safety Population: Phase 1b
14.3.2	Select Grade 3 or 4 Treatment-Emergent Laboratory Toxicities, All Cycles, Safety Population: Phase 1b
14.3.3	Electrocardiogram by Worst QTcF Results: Phase 1b
Listings	
16.2.1	Subject Disposition, All Patients Enrolled: Phase 1b
16.2.2.1	Informed Consent, All Patients Enrolled: Phase 1b
16.2.2.2	Subject Eligibility, All Patients Enrolled: Phase 1b
16.2.3	Analysis Populations, All Patients Enrolled: Phase 1b
16.2.4.1	Demographics, All Patients Enrolled: Phase 1b
16.2.4.2	General Medical History, All Patients Enrolled: Phase 1b
16.2.4.3	AML Diagnosis, All Patients Enrolled: Phase 1b
16.2.4.4	Additional AML Details, All Patients Enrolled: Phase 1b
16.2.4.5	Prior Systemic Anti-Leukemia Regimens, All Patients Enrolled: Phase 1b

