16.2.5.1	Drug Accountability, All Patients Enrolled: Phase 1b
16.2.5.2	Exposure Dosing Log, All Patients Enrolled: Phase 1b
16.2.5.3	Cycle Day 1 Dose, All Patients Enrolled: Phase 1b
16.2.5.4	Pharmacokinetic Sampling, All Patients Enrolled: Phase 1b
16.2.5.5	Prior and Concomitant Medications, All Patients Enrolled: Phase 1b
16.2.5.6	Bone Marrow Transplant Post-Study Treatment, All Patients Enrolled: Phase 1b
16.2.6.1	Response Assessment, All Patients Enrolled: Phase 1b
16.2.6.2	Bone Marrow Examination, All Patients Enrolled: Phase 1b
16.2.6.3	Relapse/Progression Assessment, All Patients Enrolled: Phase 1b
16.2.6.4	Relapse Assessment Continued, All Patients Enrolled: Phase 1b
16.2.6.5	Survival Status, All Patients Enrolled: Phase 1b
16.2.7.1	Adverse Events, All Patients Enrolled: Phase 1b
16.2.7.2	Serious Adverse Events, All Patients Enrolled: Phase 1b
16.2.7.3	Deaths, All Patients Enrolled: Phase 1b
16.2.8.1	Laboratory Toxicities – Select Hematology Analytes, All Patients Enrolled: Phase 1b
16.2.8.2	Laboratory Toxicities – Select Serum Chemistry Analytes, All Patients Enrolled: Phase 1b
16.2.8.3	Vital Signs, Height, and Weight, All Patients Enrolled: Phase 1b
16.2.8.4	Physical Examinations – Abnormal Findings, All Patients Enrolled: Phase 1b
16.2.8.5	ECG Central Reading – Triplicate, All Patients Enrolled: Phase 1b
16.2.8.6	Echocardiogram/MUGA, All Patients Enrolled: Phase 1b

16.2.8.7	ECOG Performance Status, All Patients Enrolled: Phase 1b
----------	--

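### The only planned response table omits dosed patients who stop before the first response assessment for reasons other than toxicity or death; an all-dosed companion table would show whether this matters

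*SAP*

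**What the plan says.** SAP 5.5 puts a patient in the EE set if they received at least one dose of either study drug and they "complete the first protocol-specified response assessment or have discontinued study treatment for toxicity or die prior to the first response assessment". Protocol 15.2.1 has the same rule, so the two documents agree.

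SAP 6.5 summarises best response on the EE population and then states: "Patients with no post-baseline response assessments will be considered non-responders". Exact 95% confidence intervals are planned for the CR/CRh rate and for the any-CR rate (CR, CRh or CRi).

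The one response table in SAP section 10 is 14.2.1, "Summary of Best Response by ELN 2017 response criteria, Efficacy Evaluable Population: Phase 1b". The overall survival table (14.2.2) uses the Safety Population. Listing 16.2.6.1 is "Response Assessment, All Patients Enrolled: Phase 1b".

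Protocol 12.1 schedules the first on-treatment marrow for response on Cycle 2 Day 1. Protocol 13.0 allows treatment to stop for several reasons besides toxicity and death, among them withdrawal of consent, need for a prohibited medication, transplantation and "Non-compliance with the study regimen".

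**The concern.** The EE rule keeps two kinds of early loss in the denominator, toxicity stops and deaths, and drops the others. A patient who withdraws or is taken off for non-compliance in Cycle 1 has usually had no chance to show a response. In an all-treated analysis that patient would be a non-responder; under SAP 5.5 the patient is not counted.

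Protocol 4.1 expects some patients to leave before the end of the DLT period for reasons other than a DLT and provides for extra enrolment to make up the DLT-evaluable number. That restores the DLT count but does not return the patient who left to the response denominator.

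At stake is how the Phase 1b response rates are read. Results are reported by dose level, some groups may hold only a handful of patients, and a single omission shows in the rate. No all-treated response result is planned for comparison.

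**Working it through.** **Figures in the plan.** Neither document gives a number or rate of patients excluded from EE. The only efficacy figures that can be recomputed belong to the two-stage design in SAP 4.2 (12 patients, stop at 3 or fewer responders; 37 in total, reject at 13 or fewer; 23% against 46%). Exact binomial calculation gives early termination probability 0.7096, expected sample size 19.259, type I error 0.0246 and power 0.8061, against 0.710, 19.26, 0.025 and 0.806 stated. They reproduce, and this point does not touch them.

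**Does the non-responder rule close the gap?** In SAP 6.5 it directly follows the sentence that restricts the response summary to EE. Read in that order, it covers patients already in EE without an assessment, that is, toxicity stops and deaths. This is an inference from placement, since the text states no limit. If the rule was meant for all treated patients, it conflicts with SAP 5.5.

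**Effect on the rate.** Let n be the dosed patients in a dose group, x the responders, and k the dosed non-responders left out of EE.

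- All-treated rate: x/n. EE rate: x/(n − k).
- Ratio of EE to all-treated: n/(n − k), which exceeds 1 whenever k ≥ 1 and x ≥ 1.
- If x = 0, both rates are 0% and only the upper limit moves.

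The same ratio applies to CR/CRh and to any-CR.

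**Illustrations.** All responder and exclusion counts are assumed. The 3 to 6 patients of the 3 + 3 scheme and the maximum of 20 per dose cohort are in SAP 2.1. The 3 and 6 are counts of DLT-evaluable patients, and a patient who stops early without a DLT is replaced (Protocol 4.1 and 13.0). One exclusion in a six-patient group is therefore typically 7 dosed and 6 in EE. Intervals are exact (Clopper-Pearson) 95%.

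| Setting | All dosed | EE | Shift |
|---|---|---|---|
| Small cohort, 1 left out | 2/7 = 28.6% (3.7–71.0) | 2/6 = 33.3% (4.3–77.7) | 4.8 points |
| Cohort of 20, 1 left out | 5/20 = 25.0% (8.7–49.1) | 5/19 = 26.3% (9.1–51.2) | 1.3 points |
| Cohort of 20, 2 left out | 5/20 = 25.0% (8.7–49.1) | 5/18 = 27.8% (9.7–53.5) | 2.8 points |

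With no responder, the exact upper limit is 1 − 0.025^(1/n). For 0/7 it is 41.0% and for 0/6 it is 45.9%, so the EE interval is wider at the top while the rate stays at 0%.

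**Size against precision.** The all-dosed interval for 2/7 spans 71.0 − 3.7 = 67.3 points and that for 5/20 spans 49.1 − 8.7 = 40.4 points. The shifts are small beside these.

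**The case against.** The case against acting has four parts.

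*Much is already handled.* Toxicity stops and deaths stay in EE. SAP 6.1 reports the numbers treated, the reasons for stopping treatment and the size of each analysis population by treatment group. Listings 16.2.1, 16.2.3 and 16.2.6.1 cover all enrolled patients, so a reader could mostly rebuild the all-treated rate and infer why a patient fell out of EE. This stands, and it is the main reason the point is minor. What is not planned is the all-treated result itself, with its interval.

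*No decision depends on it.* SAP 4.1 sets no formal hypothesis, SAP section 7 says Phase 2 was not enrolled, and response is a secondary endpoint in Phase 1b. This also stands.

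*Early progressors may not be lost.* A reader might infer that patients who progress in Cycle 1 are systematically dropped. The documents do not support that. Protocol 12.0 says: "Assessments that define the quality of response to study treatment will include physical examination, peripheral blood counts, and bone marrow examination". Protocol 12.1 adds: "At other times, perform bone marrow examination for confirmation of suspected progression/relapse". Appendix 2 opens its definition of progression with "Evidence for an increase in bone marrow blast percentage and/or circulating blast counts as defined by at least one of the following", and its criteria include circulating blasts and new extramedullary disease. Many early progressors may therefore have a qualifying assessment. SAP 5.5 does not settle the matter, so the point is limited to stops such as withdrawal or non-compliance.

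*The rule might cut the other way.* A reader might argue that it could drop a responder who missed Cycle 2 Day 1. That needs a strained reading: nothing in SAP 5.5 says only that visit counts, and a later scheduled marrow can be read as the first completed assessment.

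**Conclusion.** The point holds in a conditional form. SAP 5.5 leaves out of EE a dosed patient who stops before the first response assessment for a reason other than toxicity or death. Where such patients are non-responders and the dose group has at least one responder, the EE rates for CR/CRh and any-CR exceed the all-treated rates by the factor n/(n − k).

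The size is unknown because the number excluded is not given and may be zero. Under the assumed counts above, the shift is 1.3 to 4.8 points, well inside the confidence intervals. The conclusion also rests on reading the SAP 6.5 non-responder rule as applying within EE, which is the most natural reading but not an explicit one.

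A reader might infer that the reported response rates will be inflated, or that a conclusion about the regimen is at risk. The documents support neither. They do not show that any patient was excluded, and the rates are descriptive. Nor do the protocol and SAP disagree on this rule. Severity is minor; the change is a cheap improvement.

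**What to change.** Leave the EE definition and Table 14.2.1 as they are. Add to SAP 6.5 and section 10 a companion to Table 14.2.1 that:

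- covers all patients who received at least one dose of either study drug;
- gives best response, CR/CRh and any-CR with exact 95% confidence intervals, by dose level and overall;
- counts patients without a post-baseline response assessment as non-responders;
- shows the number excluded from EE, with reasons, by dose level.

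The all-dosed set needs its own one-line definition, because the Safety Population in SAP 5.2 also requires an on-treatment safety observation. Record the addition in SAP section 7. Protocol 15.0 lets the SAP modify the planned analyses, and the primary endpoint is not affected.

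The cost is one extra table and a reported rate that may be slightly lower; no new data are needed. If nobody was excluded from EE, the two tables agree and the question is closed.

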6. STATISTICAL METHODS

Descriptive statistical methods will be used to summarize the data from this study. Unless stated otherwise, the term “descriptive statistics” refers to number of patients (n), mean, medians, interquartile ranges, standard deviation (STD), minimum, and maximum for continuous data and frequencies and percentages for categorical data. The term “treatment group” or “dose group” refers to the dose level of LANRA. Unless otherwise specified, data summaries and analyses described below will be reported by dose group and overall, in Phase 1b. Select data collected during the study will be included in data listings. Unless otherwise noted, the data will be sorted first by dose level/cohort, patient number, and then by date within each patient number.

6.1. PATIENT DISPOSITION, DEMOGRAPHIC, AND BASELINE CHARACTERISTICS

The number of patients screened, enrolled, treated, and discontinued from study treatment and follow-up will be summarized. The primary reason for study treatment discontinuation and follow-up will be summarized for Phase 1b. The number of patients in each analysis population will be presented by treatment group.

Demographic data including age (years), sex, race, and ECOG PS will be summarized for the safety population in Phase 1b using descriptive statistics.

6.2. MEDICAL HISTORY

All clinically relevant prior or concurrent medical conditions will be mapped to a system organ class (SOC) and PT using the version of the Medical Dictionary for Regulatory Activities (MedDRA) in effect at the time of database lock. Medical history will be listed.

6.3. LEUKEMIA HISTORY

The following baseline characteristics will be summarized using descriptive statistics for patients in Phase 1b: age; months since initial diagnosis; subtype of AML at diagnosis (*de novo* AML, AML with myelodysplastic features or therapy-related AML); best response to last prior regimen (partial remission, stable or progressive disease, primary refractory disease after 1st line induction or recurrence of leukemia after CR) per ELN criteria; number of relapses (0, 1, ≥ 2); type of *FLT3* mutation (ITD, TKD or both) and allelic frequency (high, low); history of hematopoietic stem cell

transplant including post-transplant best response (if known); prior exposure to a *FLT3* inhibitor (e.g. midostaurin) and presence of other somatic mutations (e.g. *NPM1*, *IDH1*, *IDH2*, *DNMT3A*, *TP53*) at diagnosis and baseline, if known.

The number of prior systemic antileukemic regimens will be summarized. By-patient listings of systemic leukemia treatment regimens, including start and stop dates for each regimen component, will be generated for Phase 1b. Anti-neoplastic agents will be classified using 11-digit, World Health Organization (WHO) Drug Dictionary codes preferred name and the Anatomic Therapeutic Chemical (ATC) Classification for pharmacologic properties and summarized by frequency distributions for Phase 1b.

6.4. EXPOSURE TO TREATMENT

Duration of exposure, cumulative dose, actual and relative dose intensities will be summarized for LANRA and gilteritinib. Treatment interruptions, dose reductions and reasons for discontinuation of gilteritinib/LANRA will be summarized by frequency distributions and percentages.

6.5. EFFICACY ANALYSIS

Best response (CR, CRh, CRi, PR, MFLS, stable disease [SD], and progressive disease [PD]) will be summarized for the efficacy-evaluable population by frequency distributions and percentages in accordance with ELN 2017 criteria. Patients with no post-baseline response assessments will be considered non-responders. The 95% confidence interval (CI) for estimates of the proportion of patients with CR/CRh will be constructed with exact methods for the binomial distribution (eg Clopper-Pearson intervals). Additionally, 95% CIs for the estimates of the proportion of patients with any CR (CR, CRh or CRi) will be constructed in a similar manner.

Overall survival will be estimated using K-M methodology, including 95% CIs for quartiles. Minimal and maximal survival times will be computed by dose level. Patients alive at last follow-up will be censored at the date of last contact.

